9.4 Endpoint

In the present Clinical Investigation, the two variables chosen as *the primary and secondary endpoints* to measure the primary and secondary objectives of the Survey also coincide with the measures of response to treatment, in particular:

- Primary endpoint (security measure):

the safety of the *Chimaera* will be measured by the percentage of patients who within a 6-month observation period, due to serious adverse events related to *the Chimaera*, will have to undergo a second operation to continue with the treatment of the proximal femur fracture.

- Secondary endpoint (efficacy measure):

the effectiveness of the treatment carried out with *Chimaera* will be measured through the Bowers & Parker functional score for the evaluation of the patient's functional recovery.

Note:

Bowers & Parker's functional score⁷ It is a validated and unanimously recognized reliable score for the evaluation of patients treated following a hip fracture. This score assesses the patient's functional recovery (in terms of pain, walking ability and social independence) compared to the patient's condition before the fracture. The Bowers & Parker score also has predictive value for assessing the long-term mortality of the treated patient, and for planning short-term rehabilitation activities.

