9.5 Variables to measure

The primary endpoint (safety measure) of the present Clinical Investigation will be measured as follows:

- the correlation of the serious adverse event to the *Chimaera* will be freely assigned by the Investigator according to the following options: unrelated/potentially related/certainly related. Serious events potentially or certainly related to the *Chimaera* will be included in the calculation of the security measure.
- It is understood that, for serious events judged to be potentially or certainly related to the *Chimaera*, the Sponsor reserves the right to supplement the Investigator's assessment with an opinion from an independent orthopaedic physician and with a technical analysis of the implanted and removed device to proceed with the second intervention. Following these analyses, if the removed device complies with the design specifications, and if the independent orthopedist finds an operating technique error in the primary implant, in agreement with the Investigator, the event initially classified as potentially or certainly related to the *Chimaera* may be reclassified as unrelated and, therefore, will be excluded from the calculation of the safety measure. Similarly, serious adverse events due to use that does not comply with the manufacturer's instructions for use, otherwise referred to as *off label use*, will be excluded from the calculation of the safety measure.

The *secondary endpoint* (efficacy measure) of the present Clinical Investigation will be measured as follows:

- The Investigator will fill out a scale (Appendix 1) for each patient at each of the follow-up visits (1, 3, 6, and 12 months). If necessary, a translation of the scale into Italian is also provided to support comprehension.
- As suggested by the authors, the scale can be filled in by the Investigator on the basis of the answers provided by the patient, even by telephone. Given the type of patients that will be recruited, mostly non-self-sufficient elderly people who cannot always be moved easily, this procedure will not involve additional risks for the patient and should limit the number of patients that cannot be assessed due to lack of data on the secondary *endpoint*.

Data for the primary and secondary *endpoints* will be:

- reported in the patient's medical record and recorded in the electronic database provided free of charge by the Sponsor to each Investigator to collect the data of the Clinical Investigation;

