9.11 Medical-Surgical Procedures and Follow-up of the Clinical Investigation

After obtaining informed consent, the physician will include in the study those patients who, at the screening visit (Visit 0), meet all selection criteria. During the screening visit, the Investigator will also collect demographic data and the patient's medical history.

Enrolled patients, as would also occur if they chose not to participate in the present Investigation, will undergo the surgical procedure (Visit 1) required for the application of the investigational medical device (Chimaera), which marks the beginning of the treatment period.

Following the surgery, the patient will attend five subsequent visits. The first three visits after the surgical procedure are part of the treatment period and are:

- the visit performed at hospital discharge (Visit 2), which, unless complications occur, will take place within 10 days after the date of surgery. During this visit, the physician will perform routine assessments to confirm that the operation and postoperative course have proceeded appropriately;
- the following two visits (Visits 3 and 4), were conducted at 1 month and 3 months after the date of surgery, respectively. These visits conclude the treatment period which, in the absence of complications, is expected to be within 8–12 weeks from the date of surgery, with the consolidation of the treated proximal femoral fracture. Healing will be assessed by the Investigator through radiographic evaluation, performing a qualitative assessment of bone density at the fracture site and the alignment of the bone fragments. Starting from Visit 4 and at all subsequent visits, the Investigator will also complete the Bowers & Parker functional score (efficacy measure) to assess the patient's functional recovery.

For these patients, device removal is not planned unless required due to serious adverse events necessitating a second surgical procedure to complete the treatment of the fracture (safety measure). Once the treatment period is concluded, the follow-up period begins, during which two visits will be conducted (Visits 5 and 6), respectively at 6 months and 1 year after the date of surgery. During these visits, clinical data will be collected to monitor the progression of fracture consolidation, the patient's functional recovery, and the occurrence of any medium-term adverse events.

[figure not shown]

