9.12 Patient treatment schedule

9.13 Table of procedures applicable to each visit

PERIOD		ENROLMENT	TREATMENT				FOLLOW-UP	
VISIT	Number	Visit 0	Visit 1	Visit 2	Visit 3	Visit 4	Visit 5	Visit 6
	Type	Selection	Surgery	Discharge	1° Follow up	2° Follow up	3° Follow up	4° Follow up
	Window	Day 0 ± 1 week	Day 0	Day 5 ± 5 days	Month 1 ± 1 week	Month 3 ± 1 week	Month 6 ± 1 week	Month 12 ± 1 Month
Informed Consent		x						
Verification of Selection Criteria		x	x	x	x	x	x	x
Demographics		x						
Medical History		x						
Radiographic Examination		x	x			x		
Device Implantation			x					
Parker score						x	x	x
Safety Measures			x	x	x	x	x	x

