9.14 Predictable factors that can compromise results

The procedures described in this Protocol are part of the normal clinical practice of the Centers involved. In fact, this clinical investigation is observational so it will not change the clinical protocols currently in use in the Centers involved, nor does it involve additional risks for patients and investigators.

In the present clinical investigation, given the type of patients who will be enrolled, two factors are known that could compromise the outcomes and the interpretation of the results, namely:

- For some very elderly patients who have difficulty moving and with impaired cognitive ability, for example due to senile dementia or advanced neurodegenerative diseases, the assessment of functional recovery may be more difficult.

The Bowers & Parker Functional Score⁷ chosen to assess the patient's functional recovery in terms of pain, walking ability and social independence, as described by the authors, precisely because it could be used in high probability on patients unable to answer reliably, it is composed of questions that can also be answered by the patient's companion (e.g. cohabitant, family member, caregiver, social health worker, etc.), understood as a person who lives in close contact with the patient. The companion can also answer by phone and, given the difficulty of moving this type of patient, this possibility will be very useful to limit the loss of data on the patient's functional recovery in the follow-up period.

- The mortality rate of enrolled patients is about 10% at 10 days after surgery and can reach up to 36% at 1 year. Therefore, a high percentage (25% on average) of non-assessable patients, i.e. discontinued before the end of the treatment period for supposed recovery (scheduled for the check-up visit in the third month after the operation), is expected in the present clinical investigation.

In order to increase the probability of reaching the expected sample size, i.e. 300 evaluable patients, i.e. who will complete at least the scheduled follow-up visit at the third month after the operation (Visit 4), the Sponsor has planned the enrollment of 400 patients and has agreed with the Investigators on a patient replacement procedure described below.

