9.15 Interruption and withdrawal of subjects from clinical investigation

A patient will be discontinued prematurely from the study if they do not complete the last protocol-scheduled follow-up visit due to any of the following causes:

- the patient withdraws consent to participate in the study;
- one of the inclusion criteria will be dropped or an exclusion criterion will occur;
- lack of response to treatment that generates an unacceptable risk for the patient and prevents the continuation of the treatment covered by this observational scientific research;
- onset of a serious adverse event that generates an unacceptable risk for the patient and prevents the continuation of treatment;
- the patient does not follow the procedures of the clinical protocol provided by his doctor;
- decision of the Investigator in the interest of the patient;
- patient no longer available (lost to follow-up);
- death of the patient during the study period.

Patients who are prematurely discontinued will be reported in the data collection form through the appropriate discontinuation visit. The Investigator will have the obligation to report to the Sponsor the patients who are prematurely discontinued and, if the patient is not assessable, or is discontinued before the end of the treatment period for supposed recovery scheduled for the control visit at the third month after the operation), may agree with the Sponsor on the replacement of the patient according to the following procedure.

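### The telephone and companion route is written only for the functional score, so second operations by 6 months may go unrecorded in patients who cannot attend or are discontinued

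*Combined protocol and SAP*

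**What the plan says.** - **Primary endpoint (9.4).** The safety measure is the "percentage of patients who within a 6-month observation period, due to serious adverse events related to" the device, need a second operation. Section 9.5 explains how relatedness is judged and when an event may be reclassified. It does not explain how a second operation is discovered in a patient who does not come back.
- **Remote route (9.5, 9.14).** For the secondary endpoint, "the scale can be filled in by the Investigator on the basis of the answers provided by the patient, even by telephone". The stated reason is that this "should limit the number of patients that cannot be assessed due to lack of data on the secondary" endpoint. Section 9.14 extends the route to a companion and again ties it to the score: "this possibility will be very useful to limit the loss of data on the patient's functional recovery in the follow-up period".
- **Scheduled safety collection (9.11, 9.13).** The "Safety Measures" row of the visit table has six marks, which fits Visits 1 to 6 and so includes Visit 5 at Month 6. Section 9.11 says that Visits 5 and 6 collect data on fracture consolidation, functional recovery "and the occurrence of any medium-term adverse events". Neither place says whether this must be done in person or may be done remotely.
- **Discontinued patients (9.15, 9.16).** "Patients who are prematurely discontinued will be reported in the data collection form through the appropriate discontinuation visit". Section 9.16 adds that data from discontinued and replaced patients will be collected and analysed. No contact after the discontinuation visit is described.
- **Evaluable (9.14).** A patient is evaluable on completing Visit 4 at Month 3.
- **Event reporting (17).** The 24-hour duty to notify a serious adverse event starts when the Investigator becomes aware of it.

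**The concern.** The plan foresees follow-up loss in frail patients and provides against it for the secondary endpoint only. For a patient still in the study who cannot travel, the primary endpoint has a scheduled visit but no stated remote means of completing it. For a patient discontinued between Month 3 and Month 6, the plan counts the patient as evaluable while up to three months of the endpoint window are unobserved.

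A patient re-operated at another hospital could then enter the analysis as having no event. An error of this kind can only lower the reported percentage. It also sits awkwardly with the purpose of the investigation: sections 3 and 9.1 justify it as active collection to supplement passive vigilance, and reliance on Investigator awareness is partly passive. Some causes of discontinuation in 9.15, such as lack of response to treatment, plausibly go with a higher risk of re-operation, so the loss may not be random.

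**Working it through.** **Inputs from the documents.** Endpoint window 6 months (9.4); evaluable at Month 3 (9.14); 400 enrolled to give 300, with about 25% loss (9.7, 9.14); expected primary rate no more than 6%, planning target of a 95% upper limit below 10%, exact binomial method (18).

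**Step 1: reproduce the plan's figures.** With x events in n patients, the two-sided 95% exact (Clopper-Pearson) upper limit is the 0.975 quantile of a Beta(x + 1, n − x) distribution.

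| Rate | n | x | Plan | Recomputed |
|---|---|---|---|---|
| 3% | 100 | 3 | 8.518% | 8.518% |
| 4% | 100 | 4 | 9.926% | 9.926% |
| 5% | 160 | 8 | 9.614% | 9.614% |
| 6% | 250 | 15 | 9.703% | 9.703% |
| 7% | 400 | 28 | 9.958% | 9.958% |

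Enrolment: 300 / (1 − 0.25) = 400. The sample-size arithmetic is correct.

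**Step 2: room below the target at n = 300.** At 6%, x = 0.06 × 300 = 18.

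| Events | Percentage | Upper limit |
|---|---|---|
| 18 | 6.00% | 9.32% |
| 19 | 6.33% | 9.71% |
| 20 | 6.67% | 10.11% |

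From 18 events there is room for one more; the next one passes 10%. With 20 true events, one unrecorded event brings the limit down to 9.71%.

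**Step 3: effect of missed events, n = 300.** The documents give no share of missed events, so the shares here are assumptions. Recorded events = true events × (1 − share missed), rounded.

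| True events | Share missed | Recorded | Percentage | Upper limit |
|---|---|---|---|---|
| 18 (6%) | 0 | 18 | 6.00% | 9.32% |
| 18 | 10% | 16.2 → 16 | 5.33% | 8.52% |
| 18 | 20% | 14.4 → 14 | 4.67% | 7.71% |
| 24 (8%) | 0 | 24 | 8.00% | 11.67% |
| 24 | 10% | 21.6 → 22 | 7.33% | 10.89% |
| 24 | 20% | 19.2 → 19 | 6.33% | 9.71% |

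At a true 6% the limit is below 10% with or without the loss. At a true 8% a 20% loss moves it from above 10% to below.

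**Step 4: the denominator.** Section 18 does not say how unknown 6-month status is counted. Suppose 18 events are recorded and 100 of 400 patients have unknown status (again an assumption). Leaving them out gives 18/300 = 6.00%, upper limit 9.32%. Counting them as event-free gives 18/400 = 4.50%, upper limit 7.02%.

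**The case against.** The strongest reply is that safety is already planned at 6 months. That stands: it would be wrong to infer that patients still in the study have no check for a second operation. Visit 5 includes safety, and nothing requires it to be in person. What is missing is a stated remote way of doing it.

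A reader might also infer that operations at other hospitals are in fact missed. The documents do not show this. A score call covers hip pain, mobility and residence, so an Investigator could well learn of a re-operation and would then have to report it. Failed cases might equally return to the operating centre. Discontinuation for a serious adverse event is itself reportable and may be the primary event. The supportable statement is that events may be missed.

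The number a call could recover is also limited. Section 9.14 attributes the expected loss largely to mortality, and the data-rights text in 4.1 says no further data are collected for those who exercise those rights. Sections 9.15 and 9.16 are silent on later contact; they do not forbid it.

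Finally, section 18 tests no hypothesis and sets no safety threshold. This also stands: 10% is a precision target, and passing it would not be a failed test.

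None of this supplies a remote route for the primary endpoint, a 6-month status check after discontinuation, or a rule for unknown status.

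**Conclusion.** The concern holds as a gap in ascertainment. The remote route is written for the score alone, no status check at 6 months is described for patients discontinued earlier, and evaluability at Month 3 does not match a 6-month endpoint. The primary percentage may be underestimated.

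By how much cannot be computed, because the documents do not give the share of patients unable to attend, the number discontinued alive and still consenting, or the share of second operations done elsewhere. The exact limits in steps 1 and 2 are firm; steps 3 and 4 rest on assumed shares. They show that with 300 patients one or two events can decide on which side of the 10% planning target the upper limit falls. The change is worth making before data collection, and it concerns what is collected and reported, not the sample size.

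**What to change.** 1. **9.5 and 9.14.** State that any telephone or companion contact used for the score also asks fixed questions: any new operation on, or readmission for, the treated hip; its date, hospital and reason; and vital status.
2. **9.15.** Add one telephone contact at Month 6, with the same questions, for living discontinued patients who have not withdrawn consent or objected to further data collection.
3. **Counting rule.** Pass each reported second operation through the existing relatedness assessment in 9.5. Count it only if it is judged potentially or certainly related to the device and occurred within 6 months. Counting every confirmed second operation would change the endpoint defined in 9.4.
4. **Section 18.** Report the number of patients with unknown 6-month status, and give the primary percentage with and without them in the denominator.

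The cost is a few questions, one short call per reachable discontinued patient, and changes to the eCRF and protocol wording. The telephone is permitted for the score and not scheduled, so some site time is new. The reported rate may be higher as a result.

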9.6 Patients selection

An adult patient with a previously untreated proximal femoral fracture who, in the Investigator's sole judgement, has an appropriate indication for surgical treatment with Chimaera will be considered eligible for the Clinical Investigation. Patients who meet all of the following inclusion criteria and none of the exclusion criteria will qualify for enrolment in this Clinical Investigation.

9.6.1 Inclusion criteria

A patient will be considered eligible for participation if:

- directly or indirectly (through a legally acceptable representative), he/she has expressed the willingness to participate in the Investigation by signing and dating the informed consent form;
- he/she is at least 65 years of age at the time of signing the informed consent form;
- he/she has been diagnosed with a stable or unstable fracture in the pectrochanteric, intertrochanteric, or subtrochanteric region of the femur, not previously treated;
- in the opinion of the Investigator, he/she has a standard indication for surgical treatment with an intramedullary nail;
- the fracture will be treated with the short (length = 180 mm) Chimaera nail and one or two telescopic cephalic screws, in accordance with the manufacturer's instructions for use.

9.6.2 Exclusion criteria

A patient will be considered not eligible for participation if:

- he/she is undergoing surgery to address the sequelae of a previously treated fracture;
- he/she has been diagnosed with a pathological fracture of oncologic origin (primary tumour or skeletal metastasis);
- he/she has been diagnosed with a fracture in the diaphyseal and/or distal region of the femur;
- he/she has been diagnosed with an open proximal femoral fracture (type II or III according to the Gustilo and Anderson classification);
- he/she has been diagnosed with multiple fractures (including bilateral proximal femoral fractures);
- during the preoperative or intraoperative phase, it is decided to treat the fracture with the long version of the Chimaera nail and/or with non-telescopic (fixed-length) cephalic screws;
- he/she has a medical condition that constitutes a contraindication to treatment with Chimaera according to the manufacturer's instructions for use;
- he/she has a suspected or confirmed hypersensitivity/allergy to any component of the device that comes into contact with the patient;
- he/she presents with any clinical condition that, in the opinion of the Investigator, could interfere with the Clinical Investigation procedures or compromise patient safety;
- he/she is concomitantly treated with a non-permitted device that cannot be removed without compromising patient safety;
- he/she is participating in another clinical study or has participated in another clinical study within 3 months prior to signing the informed consent form.

9.7 *Expected Number of Patients to be Enrolled*

Considering the high proportion (approximately 25%) of anticipated premature withdrawals in this patient population, in order to obtain a sample of 300 patients completing the Investigation, a total of 400 patients are planned to be enrolled across 8 sites. Accordingly, each site is expected to enrol approximately 50 patients over a period of 6–8 months (estimate based on the current frequency of Chimaera use as reported by the sites during the feasibility phase).

9.8 *Enrolment Timepoint*

Each eligible patient able to provide consent personally will be considered enrolled in the Clinical Investigation at the time of signing and dating the informed consent form, in accordance with the procedures for collection described in this Protocol.

It is understood that patients unable to provide consent personally will be considered enrolled in the Clinical Investigation at the time of signature by the legally acceptable representative.

9.9 *Expected Number of Medical Devices to be Used*

Considering the observational nature of the Investigation and that, according to the selection criteria, only one medical device under observation (Chimaera) may be applied to each patient, in line with the expected number of patients to be enrolled, a total of 400 devices are planned to be used across 8 sites. Accordingly, each site is expected to use approximately 50 devices.

9.10 Duration of the Clinical Investigation

The duration of the Investigation for each patient is 12 months, from the signing of the informed consent form to the last follow-up visit.

Considering that the enrolment period is expected to last 6–8 months, the overall anticipated duration of the active phase of the study is 18–20 months, from the signing of the informed consent form by the first enrolled patient to the last follow-up visit of the last enrolled patient.

It is understood that, following the closure of the active phase of the study, unless otherwise agreed with the Investigators and/or Ethics Committees, the Sponsor reserves a period of 6 months to conduct the end-of-study activities, namely:

- database review;
- opening and resolution of potential data clarification requests (queries) to the Investigators;
- preparation of the statistical report;
- preparation of the clinical report;
- site close-out visits;
- end-of-study notifications to the relevant Ethics Committees and Competent Authority.

